### Skin Irritation

The following 0-to-4-point scale will be used to quantify the redness of the skin after tape removal:

Grade	Erythema/Irritation
0	None - natural skin tone
1	Slight - Barely visible increase in pink coloration
2	Mild - Visible increase in light pink coloration
3	Moderate - Diffuse pink coloration, localized or diffuse areas of reddened skin
4	Severe - Intense redness, diffused or localized

The average for each population group will be obtained after data has been collected from participants.

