Thermotape High-adhesion Medical Tape Comparison Study

June 21, 2022

Background:

Currently, modern medical tapes can be classified into two categories, high-adhesion tape, and low-adhesion tape. Both tapes, however, are not sufficient for use in a medical environment; high-adhesion tape, when removed, can cause medical adhesive related skin injuries (MARSI), which is liable to cause patients to have to return to the hospital to treat it, resulting in a dramatic increase in medical expenses once fully recovered. Conversely, low-adhesion tape is ill-suited for securing medical devices, such as IV lines, in place because of having low adhesion. As a result, a patient's ability to recover is impacted, overall increase medical expenses from an extended stay at the hospital.

Thermotape is designed to combat both flaws, by acting as a high-adhesion tape until heated, where it can be removed as easily as low-adhesion tape.

Objective:

This objective of this study is to compare the safety and performance of Thermotape compared to Tegaderm™ tape and Kind™ tape over the course of 24 hours. In regard to safety, pain inflicted during removal and any potential effects will be monitored for Thermotape versus Tegaderm™ and Kind™ tape.

Design:

A single blinded comparative clinical study, where researchers will know the tape being applied while the subjects do not.

Methods:

Consent will be obtained from the subject as they enter the building for tape application. This will be done by providing a paper consent form detailing the necessary details concerning the trial. If consent is obtained, they will be allowed into the room for tape application.

Before tape application, both forearms will be cleaned using an isopropyl alcohol wipe and skin markers will be used to draw lines, with two inches of spacing between, to separate areas of tape application. The marks began at the elbow and continued down the forearm. Following the pre-tape preparations process, Thermotape, Kind™ tape, and Tegaderm™ tape will be applied horizontally, in vertical

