succession. Following Thermotape's application, a finger will be used to rub Thermotape in a vertical motion to ensure that the tape, especially edges, are fully adhered. The same procedure will be used for Kind™, however Tegaderm™ will not require the same adhesion procedure, as noted by a nurse practitioner. The tapes will be applied in a random order. Once all tapes are applied, researchers will give the following speech: "Now that the tapes have been applied, please do not do any physically extraneous activities, like swimming in the ocean, running a marathon, or storm chasing. Basically, any activities that make you sweat. Additionally, please do not shower until we remove the tapes, even if you really want to. If you do end up getting the tapes wet, through sweat or by showering, please note it down in the activity log on the back of your activity log. Also, try not to pick at the tapes, even if the corners start lifting. Thank you and we'll see you back tomorrow!" The speech requests that subjects are to not participate in strenuous physical activity or shower for the duration of the 24-hour study. One researcher is to apply the tape to the participants. Each tape will be cut 1 inch wide by 2 inches long.

When subjects return for tape removal, they will be given a pain survey, with a 0-to-10 Wong-Baker scale, to fill out after each piece of tape is removed. One photo will also be taken of the forearms to document the state of the subject's forearms 15 minutes after tape removal. Each piece of tape is then to be analyzed for wear using a 0-to-7 point scale.

When removing the tapes, an edge will first be lifted and then it will be peeled at an angle of 180° at a consistent rate. If a hair is encountered, the tape will be removed following the root of the hair to its tip. After the removal of each piece of tape, it will be placed on a glass slide and taped down for later quantification of cell and hair counting caused by tape removal. No gloves will be used throughout the process. During removal, if a subject shows signs of extreme discomfort or the skin appears to start tearing, manual removal will be stopped and a commercial silicon-based remover, Brava, will be used to remove the tape instead. To do so, Brava will be rubbed all over the tape, including the edges, and under the skin after removal of the tape. Gloves will be used in the case of using Brava to remove tape.

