Removal of tape from both forearms will stay consistent, however one forearm (left), will use a Dynarex heat pack to assist in tape removal. Prior to heat pack activation, a corner for each tape sample will be lifted. After, the heat pack will be activated and kneaded for one minute before application onto the subject's skin. Then, the heat pack will be folded in half and applied to each piece of tape for 30 seconds before removal. The heat pack will be kneaded for 20 seconds between each tape removal.

Following the removal of all pieces of tape, the pain survey is collected, and each subject will be asked to wait 15 minutes following removal to examine for any redness that may have occurred. A 0-to-4 point scale will then be used to assess for erythema present on the forearms.

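### In the available text, the skin after removal is graded by eye only for redness and the 15-minute photo has no planned reading, so a visible tear, break or blister after a completed peel has no outcome

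*SAP*

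**What the plan says.** **Rationale and safety aim.** The protocol's Background states that "high-adhesion tape, when removed, can cause medical adhesive related skin injuries (MARSI"). The Objective then says, of safety, that "pain inflicted during removal and any potential effects will be monitored for Thermotape versus Tegaderm™ and Kind™ tape". It does not define those effects beyond pain.

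**The examination.** At the end of the protocol's Methods, "each subject will be asked to wait 15 minutes following removal to examine for any redness that may have occurred", and then "A 0-to-4 point scale will then be used to assess for erythema present on the forearms". The SAP makes this a primary result under Skin Irritation: "The following 0-to-4-point scale will be used to quantify the redness of the skin after tape removal". Each grade from 0 to 4 is described by how pink or red the skin is, and the grades are averaged by group.

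**The photo.** Methods also plans that "One photo will also be taken of the forearms to document the state of the subject's forearms 15 minutes after tape removal". Neither the protocol nor the available SAP text says who reads it, against what criteria, or where the result is reported.

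**Other skin-related measures.** The SAP's Secondary Results include cells counted on each removed strip, hairs counted, and TEWL by probe on a taped and an untaped area. All are averaged.

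**Tearing during the peel.** Methods treats the start of tearing as a reason to stop manual removal and use a remover. The available text does not list such events as an outcome.

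**The concern.** The harm that motivates the product is injury to the skin, but the only visual scale measures its colour. A torn, broken or blistered site receives whatever grade its redness earns, and nothing in the record marks it as injured. At the end, the sponsor could report mean redness, mean pain, mean cell and hair counts and mean water loss for each tape. It could not say how many subjects had a visible skin injury under any of them, which is the first thing a reader of the Background will ask.

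The point concerns strips peeled by hand to completion. Strips whose peel is interrupted and finished with the remover are a separate matter.

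**Working it through.** The plan states no figure to reproduce: there is no sample size, injury rate, alpha or power in the available text. The check is mainly a comparison of what is measured with what would have to be recorded.

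**Step 1. List every planned skin-related measure and ask whether it would identify an injured site.**

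| Measure | Source | Identifies a visible tear, break or blister? |
|---|---|---|
| Erythema grade 0-4, averaged | Protocol, Methods; SAP, Skin Irritation (primary) | No. Every grade is a colour description |
| Photo at 15 minutes | Protocol, Methods | It might show one, but no reading is planned |
| Pain 0-10, averaged | SAP, Pain experienced from Removal (primary) | No. It is the subject's report of pain |
| Cells on the strip, averaged | SAP, Skin Cells (secondary) | No. An indirect measure of stripping |
| Hairs on the strip, averaged | SAP, Hair Follicles (secondary) | No |
| TEWL, averaged by brand | SAP, Trans-epidermal Water Loss (secondary) | No. An indirect measure at the site; time relative to removal not stated |

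Result: one visual grade, limited to colour; one photo without analysis; indirect measures reported as means; no outcome for tear, broken skin or blister.

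**Step 2. What a count could show.** Assume *n* subjects, one site per subject for a given tape and forearm, independent subjects, and a true injury rate *p*. Both *n* and *p* are assumptions.

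Chance that at least one injured site occurs, 1 − (1 − p)^n, at p = 5%:
- n = 20: 1 − 0.95^20 = 64%
- n = 50: 1 − 0.95^50 = 92%

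This is the chance that an injury occurs, not that a photo shows it.

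Upper 95% exact limit when no injury is seen:

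| n | One-sided, 1 − 0.05^(1/n) | Upper end of two-sided interval, 1 − 0.025^(1/n) |
|---|---|---|
| 20 | 13.9% | 16.8% |
| 30 | 9.5% | 11.6% |
| 50 | 5.8% | 7.1% |

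**Step 3. Would a formal paired test be worth adding?** With 5 discordant pairs all in one direction, the two-sided exact McNemar p-value is 2 × 0.5^5 = 0.0625. With 6 it is 2 × 0.5^6 = 0.031. At least 6 are therefore needed. At 5% against 0%, the chance of 6 or more events is about 0.03% with 20 subjects and 3.8% with 50. Three tape pairs on two forearms would also make six tests. A descriptive summary is the useful form.

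**The case against.** The strongest reply is that the plan does look beyond redness. That is right, and it limits the point in several ways.

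- **A reader might infer that colour is the only reading of the skin, or that stripping is never reported.** The documents do not support either. TEWL is planned on the taped area, and cells on each strip are counted and averaged as a named secondary result. Both reflect stripping, though indirectly.
- **A reader might infer that skin safety will be concluded from redness alone, or that a harmful tape would look as safe as the others.** Pain is also a primary result, and a tape that strips more skin could be expected to leave more cells on the strip and possibly to raise TEWL. What stands is narrower: an isolated tear or blister can be diluted in an average and is never identified as an injury.
- **A reader might infer that an injured site would be graded 0.** That is hypothetical. Grades 3 and 4 allow for localized redness, so a small inflamed site may score high. The sound point is that the site would not be labelled as injured, whatever its grade.
- **Manual removal stops if tearing starts to appear.** Completed peels are therefore largely those in which no tear was noticed. This narrows the gap to damage missed during the peel and to blisters, but does not close it.
- **The photo may not show the lesion.** One photo of the forearms can miss small damage. That is why it should serve as a check on the examination rather than the sole source.

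Part of the SAP before Primary Results and one figure were not available, and they could contain something relevant.

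**Conclusion.** The point holds in this form: in the available text, visible injury other than redness after a completed peel has no outcome, and the photo that might show it has no planned reading. Following the plan exactly would leave the motivating harm uncounted, so this is more than a missing detail of wording.

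Its size cannot be fixed from the documents. Under the assumed values, a study of 20 subjects with no injuries could exclude only rates above 13.9% (one-sided 95%), and one of 50 only rates above 5.8%. Even so, that is information the current plan does not produce. The conclusion rests on the text available and does not imply that the planned measures are wrong or that any tape causes such injuries. It is a cheap improvement.

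**What to change.** Add one safety summary to the SAP's Skin Irritation section:

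- At the 15-minute examination already planned, record yes or no for each strip site: any visible skin injury other than redness (tear, broken skin, blister). Check the entry against the photo already taken.
- For each tape, report the number and proportion of subjects with an injured site, separately for the heated and unheated forearm, with exact 95% intervals. Place this next to the mean erythema grade.
- State that mean redness will not be described as showing absence of skin injury.
- Keep the summary descriptive, without a between-tape test.

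**Cost.** One tick-box per site, a few lines of SAP text and one small table. No new visit or procedure is needed, and the removal procedure is unchanged. The downside is that events may be rare, so the intervals will be wide, and a single photo may miss small lesions.

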## **Secondary Results:**

### Skin Cells

To prepare cells for examination, the cells on the tape will be transferred to a glass slide and heat fixed. After, one drop of methylene blue will be added to the center of the slide and a glass slide cover will be gently placed on the dye. A paper towel is then used to diffuse the excessive dye out of the slide cover. An optical microscope will then be used to examine for skin cells at 10x magnification.

Five images will be taken from each tape and an algorithm will be used to count the number of cells within the image. An average will be taken for each population group.

### Tape Wear

The following 0-to-7-point scale will be used to examine the wear of the tape when subjects come in for tape removal:

Grade	Wear/Adhesion Description
0	Test strip off
1	Test strip almost off
2	$\frac{3}{4}$ of test strip off
3	$\frac{1}{2}$ of test strip off
4	$\frac{1}{4}$ of test strip off
5	3 to 4 edges lifted
6	1 to 2 edges lifted
7	All corners adhered

An average will be taken for the tapes to determine how much wear is experienced for tape brand. An activity log will also be collected from each participant to determine the probable cause of tape wear if a grade three or below are obtained.

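### The activity log is used to find a cause only for strips at grade 3 or below, so wetting may be named as a cause of detachment when it is just as common among strips that held

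*SAP*

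**What the plan says.** The SAP, under Secondary Results, Tape Wear, grades each strip from 0 (off) to 7 (fully adhered); grade 3 means that half the strip has come off. Two things are planned with these data.

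- A summary by brand: "An average will be taken for the tapes to determine how much wear is experienced for tape brand". No condition is attached to it.
- An explanation of failures: "An activity log will also be collected from each participant", and its stated purpose is "to determine the probable cause of tape wear if a grade three or below are obtained".

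The Protocol, under Methods, shows what the log is asked to capture. Subjects are told "please do not shower until we remove the tapes" and to avoid activities that cause sweating. They are then told: "If you do end up getting the tapes wet, through sweat or by showering, please note it down in the activity log". Picking at the tapes is discouraged in the same speech, but subjects are not asked there to record it.

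Each subject wears all the brands: "Thermotape, Kind™ tape, and Tegaderm™ tape will be applied horizontally". The Protocol's Design section masks subjects to the tape but not researchers. Neither document says how a log entry becomes a probable cause, who makes that judgement, or how often wetting is expected.

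**The concern.** A cause cannot be judged from exposure among failures alone. To say that wetting contributed to detachment, one needs to know whether it was more common among participants whose strips failed than among those whose strips held. The plan triggers the look-up by the outcome and states no such comparison, although the logs needed for it will be in hand.

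A second limit comes from the design. The log belongs to the participant, and the speech does not ask which strip got wet. One entry therefore applies to every strip that person wears, and by itself it cannot explain why one brand came off while another held on the same subject. If one brand is lifted by water and its neighbour is not, that is a difference between the tapes.

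What is at stake is the reading of failures. Thermotape is presented in the Protocol's Background as highly adhesive until heated, and tape wear is the result in the SAP text that bears on adhesion. A detachment put down to wetting tends to be read as less the tape's fault, and the planned look-up could not show whether that reading is right.

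**Working it through.** The plan gives no figure to reproduce on this point. Part of the SAP was not available to read, so nothing is inferred from the absence of a sample size. All rates below are assumptions, used to show a range.

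**Inputs**

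- From the SAP: the log is collected from everyone; its stated use applies at grade 3 or below.
- From the Protocol: wetting is self-reported and discouraged, so it may be uncommon.
- Assumed: *q*, the share of participants who log wetting; *RR*, the risk of failure if wet divided by the risk if dry; *k*, the number of participants with at least one strip at grade 3 or below (called failures here).

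**Step 1. Share of failures with a wet log**

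Share = *q·RR* / (*q·RR* + 1 − *q*). With no effect, *RR* = 1 and the share reduces to *q*. So *q* = 0.05, 0.10, 0.30 and 0.50 give 5%, 10%, 30% and 50% of failures with a wet entry, while the true relative risk is 1.

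**Step 2. Chance that at least one failure has a wet log when wetting has no effect**

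Chance = 1 − (1 − *q*)^*k*.

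| *q* | *k* = 3 | *k* = 5 | *k* = 10 |
|---|---|---|---|
| 0 | 0% | 0% | 0% |
| 0.05 | 14% | 23% | 40% |
| 0.10 | 27% | 41% | 65% |
| 0.30 | 66% | 83% | 97% |
| 0.50 | 88% | 97% | 99.9% |

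This is the chance that an opportunity to name wetting arises. It is not the chance that wetting is named, because the SAP states no rule for that.

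**Step 3. Failures alone cannot tell no effect from a real one**

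A wet share of 40% among failures arises in each of these cases:

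- *q* = 0.40, *RR* = 1: 0.40 / (0.40 + 0.60) = 0.40
- *q* = 0.25, *RR* = 2: 0.50 / (0.50 + 0.75) = 0.40
- *q* = 0.182, *RR* = 3: 0.546 / (0.546 + 0.818) = 0.40

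**Step 4. What the logs of all participants add**

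Take an assumed 40 participants, of whom 8 have a failure, in the first two cases of Step 3. In both, 40% of the 8 failures (3.2) have a wet log and 4.8 do not.

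| Case | Wet | Dry | Failed if wet | Failed if dry | Ratio |
|---|---|---|---|---|---|
| *q* = 0.40, no effect | 16 | 24 | 3.2/16 = 20% | 4.8/24 = 20% | 1 |
| *q* = 0.25, real effect | 10 | 30 | 3.2/10 = 32% | 4.8/30 = 16% | 2 |

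The planned look-up sees the same thing in both rows: 3.2 wet logs among 8 failures. Only the denominators, which come from the participants whose strips held, separate them.

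**The case against.** The strongest reply is that little depends on this. The brand averages are unconditional, and nothing in either document excludes, re-grades or adjusts a strip because of a log entry. Wear is listed as a secondary result, behind pain and skin irritation. Because each subject wears all brands, a wet entry is shared across them, which makes it harder to excuse one brand and leaves the comparison of averages largely balanced on wetting. The log comes from everyone, so the comparison could be made later in any case. All of that stands, and it limits the point to how failures are explained.

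Three stronger readings are tempting, and the documents do not support them.

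- *Wetting will be named as a cause.* The SAP speaks only of a probable cause and gives no rule that a wet entry settles it. With no effect, the chance that any failure even has a wet log runs from 0% to nearly 100% over the assumed values, and subjects are told to avoid wetting.
- *Failures will be discounted in the results.* No such step is written. The text does not rule it out, but that makes it a risk and not a plan.
- *Causes will be assigned unevenly by unmasked staff.* The Protocol says that researchers know the tape. The SAP does not say who reads the log or whether brand is considered.

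It is also fair to say that the log may record more than wetting. The form is not reproduced in the text, and wetting is only the item that the speech asks subjects to note.

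What the reply does not answer is that the SAP states a method for finding a cause, and that method cannot distinguish a cause from a coincidence.

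**Conclusion.** The point holds in limited form. Using the log only for strips at grade 3 or below means that wetting may be named as a cause of detachment even when it is equally common among strips that held. With no effect, the share of failures open to that label equals the share of participants who log wetting. That equality is an identity and assumes only that wetting and failure are unrelated; its actual size cannot be given, because the documents state no wetting rate. If wetting is as rare as the instructions intend, the share is small (5% at an assumed *q* of 0.05).

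The planned brand averages stand as written. The weakness lies in the explanation of failures on a secondary result, and it is worth correcting because the correction needs no new data.

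**What to change.** In the SAP, under Tape Wear, replace the outcome-triggered look-up with the following:

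- Code every participant as wet or dry from the activity log before the wear grades are seen.
- For all participants, tabulate by tape and by logged wetting (yes or no) the number of strips, the wear grades, and the count at grade 3 or below. Give the number of participants in each group as well, since strips on one person share a log.
- Make any statement about the cause of wear from that comparison, including how the tapes differ within the same subjects.
- State that all grades stay in the brand averages, whatever the log says.

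The cost is a short change of text and one descriptive table. The wet group may be too small to support any conclusion, since wetting is discouraged. The table would show that openly, and the report should then name no cause.

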### Hair Follicles

Visual inspection will be used to count the hairs removed from tape removal. This will be averaged for each brand of tape.

### Trans-epidermal Water Loss (TEWL)

A TEWL probe, Delfin, will be used to collect local water loss on the area of where tape is applied and an area where tape was not applied. The collected values will be averaged to determine how much water is loss for each brand of tape.
